### **6.2.4 Early Terminations Assessments**

For the analysis early withdrawal visits will be assigned to the next scheduled visit where the relevant variable would have been assessed. For example subjects withdrawing after MAD week 5 will have their withdrawal visit assigned as follows: vital sign data assigned to MAD week 6 but laboratory data assigned to MAD week 9.

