Time Window	±1d	±1d	±1d	±1d	±1d	±3d	±3d	±3d	±3d	±3d	±3d	±3d	±3d	±3d	±3d
Administrative															
Concomitant medications	✓	✓	✓	✓	✓	✓	✓	✓	✓	✓	✓	✓	✓	✓	✓
IMP administration (IV) ^{d)}	✓			✓		✓	✓	✓	✓	✓	✓	✓	✓	✓	✓
Safety Assessments															
Physical examination ^{e)}	✓									✓					
Triplicate 12-lead ECG	✓									✓					
Vital signs (pulse rate, BP, RR, temperature, pulse oximetry) ^{g)}	✓		✓	✓		✓	✓	✓	✓	✓	✓	✓	✓	✓	✓
Liver ultrasound including hepatic elastography	(✓) ^{g) h)}														
Platelet count ^{f) g) i)}	✓		✓ ^{k)}	✓		✓	✓	✓	✓	✓	✓	✓	✓	✓	✓
Clinical laboratory assessments ^{f) g) j)}	✓ ^{l)}	✓	✓	✓	✓	✓	✓	✓	✓	✓	✓	✓	✓	✓	✓
Cardiac troponin ^{f) g) k)}	✓					✓		✓				✓			
Complement assessments ^{f) g) k)}	✓					✓		✓				✓			
Coagulation assessments ^{f) g) m)}	✓		✓	✓		✓	✓	✓	✓	✓	✓	✓	✓	✓	✓
Erythrocyte sedimentation rate ^{f) g) m)}	✓		✓	✓		✓	✓	✓	✓	✓	✓	✓	✓	✓	✓
Urinalysis (dipstick) ^{g)}	✓					✓		✓				✓			
Urine pregnancy test ^{g) n)}	✓							✓				✓			
Collect AEs/SAEs	✓	✓	✓	✓	✓	✓	✓	✓	✓	✓	✓	✓	✓	✓	✓

MAD PART															
Trial Period	Multiple Dose Treatment Period ^{a) b)}														
Time Point: Day (D)/Week (W)	MAD W1			MAD W2		MAD W3	MAD W4	MAD W5	MAD W6	MAD W7	MAD W8	MAD W9	MAD W10	MAD W11	MAD W12
	D1 ^{c)}	D2	D4	D8	D11										
Time Window	±1d	±1d	±1d	±1d	±1d	±3d	±3d	±3d	±3d	±3d	±3d	±3d	±3d	±3d	±3d
PK Assessments															
Blood sample for PK	✓ ^{o)}	✓		✓											✓ ^{o)}
Blood sample for anti-drug antibodies	✓									✓					
Blood sample for metabolic profiling															✓ ^{p)}
24-hour urine collection for metabolic profiling															✓ ^{q)}
PD/Exploratory Efficacy Assessments															
Blood sample for biomarkers (optional) ^{g)}	✓									✓					
PROMIS and GAS questionnaires ^{g)}	✓									✓					
EAT-10 Dysphagia questionnaire ^{g)}	✓														
Respiratory function ^{g) r)}	✓			✓						✓					
MyoGrip ^{g) r)}	✓									✓					
MFM32 ^{g) r)}	✓									✓					

AE: adverse event; BP: blood pressure; EAT-10: Eating Assessment Tool; ECG: electrocardiogram; EoT: End of Treatment; FU: follow-up; GAS: Goal Attainment Scaling; IMP: investigational medicinal product; IPF: immature platelet fraction; IV: intravenous; MAD: multiple ascending dose; MFM: Motor Function Measure; PD: pharmacodynamics; PK: pharmacokinetics; PROMIS: Patient Reported Outcomes Measurement Information System; RR: respiratory rate; SAE: serious adverse event.

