PROMIS and GAS questionnaires ^{f)}	✓						✓						✓	
CGI-I and PGI-C questionnaires ^{f)}	✓												✓	
EAT-10 Dysphagia questionnaire ^{f)}	✓												✓	
Respiratory function ^{f) m)}	✓						✓						✓	
MyoGrip ^{f) m)}	✓						✓						✓	
MFM32 ^{f) m)}	✓						✓						✓	
Muscle biopsy ^{m)}	✓ ⁿ⁾												(✓) ^{o)}	

AE: adverse event; BP: blood pressure; CGI-I: Clinical Global Impression of Improvement; EAT-10: Eating Assessment Tool; ECG: electrocardiogram; ED: early discontinuation; EoT: End of Treatment; FU: follow-up; GAS: Goal Attainment Scaling; IMP: investigational medicinal product; IPF; immature platelet fraction; IV: intravenous; MAD: multiple ascending dose; MFM: Motor Function Measure; PD: pharmacodynamics; PGI-C: Patient Global Impression of Change; PK: pharmacokinetics; PROMIS: Patient Reported Outcomes Measurement Information System; RR: respiratory rate; SAE: serious adverse event.

- Where possible, the visits in the MAD extension part will take place on the same day of the week as MAD Week 1 Day 1. A window of ±3 days is allowed, with a minimum of 4 days between 2 subsequent infusions. Assessments of a single visit can be split over 2 consecutive days, if required.
- If a subject is NOT on treatment after the trial, the subject will return to the clinic 3 months after the last IMP administration, to follow-up on the subject's status including abnormal laboratory test results, AEs, and concomitant medications.
- Slow infusion over 1 hour; subjects will be monitored on site by qualified site personnel for a minimum of 1 hour after the infusion for safety.
- The subject may continue to receive IMP weekly with clinic visits every 2 weeks with assessments as defined in the Trial Schedule for Follow-up post MAD Week 25.
- A symptom-directed physical examination (and measurement of body weight at MAD Week 13) will be performed. A neurologic assessment is also to be performed at the EoT/ED and EoT FU visit.
- To be performed pre-dose.

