### **6.2.5 Duration/Study Day/Time**

Study day will be calculated as the number of days from first dose of SAD part.

- date of event – date of first dose of study drug + 1, for events on or after first dose
- date of event – date of first dose of study drug, for events before first dose.

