### 6.2.11 Unscheduled Visits

Only scheduled post-baseline laboratory and vital signs values will be tabulated. Post-baseline repeat/unscheduled assessments will be disregarded, although these post-baseline assessments will be listed in the relevant appendices to the CSR.

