### **6.14.2 Laboratory Data**

Descriptive statistics (n, mean, SD, median, min, max) of the observed values and change from baseline (continuous data) will be presented by treatment group (cohort, subcohort) and visit for each hematology, chemistry and urinalysis parameter.

Each measurement (continuous data) will be classed as below, within, or above normal range, based on ranges supplied by the laboratory used. Shift tables in relation to the normal range from baseline to the worst recorded result in each trial period will be presented.

In addition to central laboratory, platelet counts will be analyzed in local laboratory. This local laboratory data will be reported as part of the laboratory tables describe above.

All laboratory data will be listed.

Some laboratory samples are analyzed in local laboratory instead of central laboratory. If data from same sample is available from both central and local laboratory then the records from central laboratory will be used. Local laboratory might use different units and/or normal ranges to central laboratory and this need to be taken into account as described below.

For shift tables (low/normal/high) local lab data will use the original units and normal ranges.

For descriptive statistics, local laboratory results are normalized using location-scale normalization or scale normalization to be comparable to central lab results. These methods are described by Karvanen (2003).

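### SAP 6.2.4 moves early-discontinuation results to the next scheduled visit with no limit on the gap, so a PGI-C value can be tabulated 11 to 12 weeks ahead; its laboratory example also disagrees with the visit schedule

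*SAP*

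**What the plan says.** SAP 6.2.4 states that "early withdrawal visits will be assigned to the next scheduled visit where the relevant variable would have been assessed". It gives no window, maximum gap or minimum exposure. It illustrates the rule with a subject who leaves after MAD Week 5: vital signs go to Week 6, with "laboratory data assigned to MAD week 9". SAP 6.14.2 uses the term laboratory data for summaries "for each hematology, chemistry and urinalysis parameter".

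No other SAP section supplies a limit. SAP 6.2.11 ("Only scheduled post-baseline laboratory and vital signs values will be tabulated") deals only with unscheduled and repeat measurements.

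Under Protocol 6.1.5 the early-discontinuation (ED) visit uses the MAD Week 25 assessment list, which includes PGI-C, respiratory function and MFM32. The notes to the Trial Schedules say that subjects are encouraged, not required, to complete it. SAP 6.13.3 tabulates PGI-C by visit as frequencies and responders, and SAP Section 12 lists a PGI-C mean-profile figure. SAP Section 10 names FVC, MIP, total MFM32 and PGI-C as the efficacy parameters kept after the early termination of the study.

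**The concern.** A carry-to-next-visit rule does little harm when a variable is measured every week or two. It does more when the next scheduled measurement is months away. PGI-C has no scheduled measurement between MAD Week 1 and Week 12, so every ED value collected in that stretch goes into the Week 13 row whatever the number of doses received. A reader of that row would take it to describe a completed 12-week course. The same holds between Weeks 14 and 24 for the Week 25 row. Relabelling an observed value is not imputation in the strict sense, but it sits uneasily with Protocol 9.13, which rules out imputation.

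Study day does not repair this, because "Study day will be calculated as the number of days from first dose of SAD part"; it does not show how long a subject had been on weekly dosing.

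The laboratory example raises a different problem. Rule and example give different weeks for the same panels, so a programmer cannot follow both. Mean change from baseline in laboratory data is a secondary endpoint (SAP 3.2), so the discrepancy reaches beyond the exploratory outputs.

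**Working it through.** **The plan's own example.** Apply the rule (first scheduled week after Week 5) to the Protocol's MAD schedule.

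| Variable | MAD weeks scheduled, up to Week 13 | Next after Week 5 | SAP example |
|---|---|---|---|
| Vital signs | every week | 6 | 6, agrees |
| Chemistry, hematology, platelets, coagulation, ESR | every week | 6 | 9 if read as laboratory data, disagrees |
| Urinalysis, troponin, complement | 1, 3, 5, 9, 13 | 9 | 9, agrees |

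The example is right for vital signs and for the sparsely sampled panels. It is wrong by 9 − 6 = 3 weeks for the weekly ones. Of the three panels that SAP 6.14.2 calls laboratory data, two (hematology and chemistry) are misplaced.

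**Size of the shift for the retained efficacy variables.** The documents do not fix when the ED visit takes place, so two timings are shown.

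- Timing A (assumption): ED visit one week after the last dose. The ED week is w = 2, …, 25, with w − 1 MAD doses received. Shift = (first scheduled week ≥ w) − w.
- Timing B (assumption): ED visit in the week of the last dose, Weeks 1 to 24. Shift = (first scheduled week after that week) − that week.

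| Variable | MAD weeks scheduled | A: stopping weeks with shift ≥ 1 week | A: largest shift | B: largest shift |
|---|---|---|---|---|
| PGI-C | 13, 25 | 22 of 24 | 13 − 2 = 11; 25 − 14 = 11 | 13 − 1 = 12 |
| FVC, MIP | 1, 2, 7, 13, 19, 25 | 19 of 24 | 13 − 8 = 5 | 13 − 7 = 6 |
| MFM32 total | 1, 7, 13, 19, 25 | 20 of 24 | 7 − 2 = 5 | 7 − 1 = 6 |

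Under timing A the zero-shift weeks are 13 and 25 for PGI-C (24 − 2 = 22), five weeks for FVC and MIP (24 − 5 = 19), and four for MFM32 (24 − 4 = 20). These are counts of possible stopping weeks, not of subjects. Week 25 is the planned end-of-treatment visit; without it the PGI-C count is 22 of 23.

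**Exposure behind the label.** Week 13 and Week 25 assessments are pre-dose, so on-schedule subjects have had 12 and 24 MAD doses. An ED value at Week 2 follows 1 dose and is labelled Week 13. An ED value at Week 14 follows 13 doses and is labelled Week 25.

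**Weight of one subject.** The target is about 6 subjects per dose level and up to 3 with an *MTM1* mutation. With all of them contributing, one reassigned response can move a responder proportion by 1/6 = 16.7 points, or 1/3 = 33.3 points in a cell of 3.

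**The case against.** The rule is explicit and deterministic, and its own example shows a multi-week move, so the gap may have been accepted knowingly. The trial is descriptive, with no hypothesis testing, and PGI-C is exploratory. The rule also keeps withdrawing subjects in the Week 13 and Week 25 rows, which would otherwise hold little more than completers. A separate early-termination row would pool values after 1 dose with values after 23. All of this stands. It limits the weight of the point, but it does not make a Week 13 label informative for a subject who had one dose. The dose comparison also leaves out the earlier SAD dose that most subjects received. That is true, but the SAD dose is common to early leavers and completers alike, apart from replacements who entered at MAD.

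The laboratory conflict lies in an illustration, and the operative sentence before it is clear. That also stands: a one-line correction is enough.

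Four stronger readings are tempting, and the documents do not support them.

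- *The safety evaluation is compromised.* Adverse events are not tabulated by visit, and all data are listed. The hematology, chemistry, coagulation, complement and ECG shift tables use the worst result in each trial period. Weeks 6 and 9 both lie in the MAD part, so the choice between them leaves those tables unchanged.
- *Subjects who leave during SAD follow-up will appear under MAD Week 13.* The wording of 6.2.4 does not bar this, but it does not state it either. The PGI-C endpoint is defined for single and multiple administration, and exposure, compliance and adverse events are reported by part. It is a gap in wording, not a demonstrated error.
- *PGI-C is on average mislabelled by 5.5 weeks.* That figure comes from weighting all 24 stopping weeks equally. No discontinuation data support such weights.
- *ED safety values fall out of the tables under SAP 6.2.11.* They do not, because 6.2.4 maps them to scheduled visits.

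**Conclusion.** The point holds in limited form. SAP 6.2.4 has no gap limit. For PGI-C it can place a value 11 weeks ahead of when it was given (ED visit one week after the last dose) or 12 weeks ahead (ED visit in the week of the last dose). For FVC, MIP and MFM32 the largest shift is 5 or 6 weeks on the same two assumptions. The laboratory example is 3 weeks out for chemistry, hematology, platelets, coagulation and ESR, and correct for urinalysis, troponin and complement.

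What is affected is descriptive: by-visit summaries, responder proportions and mean profiles. Listings, individual profiles and the planned dose counts allow a reader to trace individual cases. How many subjects are affected cannot be said: ED assessments are optional and the documents give no count. Whether both PGI-C tables survive depends on the strikethrough in SAP Section 12, which cannot be read with certainty in the extracted text; that PGI-C itself is retained is stated in SAP Section 10. The point is worth correcting because cells are small and the correction is cheap, not because any main conclusion depends on it.

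**What to change.** Revise SAP 6.2.4 in three respects.

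1. Correct the example by panel: Week 6 for chemistry, hematology, platelets, coagulation and ESR; Week 9 for urinalysis, troponin and complement.
2. State that ED results are never reassigned from the SAD part to the MAD part.
3. For PGI-C and, for consistency, FVC, MIP and MFM32, tabulate an ED value under a nominal visit only if it falls within that visit's protocol window (±3 days at Weeks 13 and 25). Otherwise show it in an early-termination row for that trial part, with the number of doses received in the part and days since the last dose. SAP study day should not be used for this.

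Leave the mapping of the safety variables otherwise unchanged; no harm from it has been shown.

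The cost is SAP wording and minor reprogramming. No new data are needed, since SAP 6.10 already plans dose counts. There are two downsides. The Week 13 and Week 25 rows will hold fewer observations: under timing A and nominal visit dates, PGI-C would leave its nominal row in 22 of 24 possible stopping weeks. The early-termination row will also pool different exposures, which is why the dose count must be shown beside each value.

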### **6.2.5 Duration/Study Day/Time**

Study day will be calculated as the number of days from first dose of SAD part.

- date of event – date of first dose of study drug + 1, for events on or after first dose
- date of event – date of first dose of study drug, for events before first dose.

### **6.2.6 Conventions for Missing and Partial Dates**

It is not expected that there will be any missing dates, however in the rare case that an AE start date or time is missing and it is unclear whether the AE is treatment emergent or not then a conservative approach will be taken and it will be assumed that the AE occurred after first dosing (earliest date of all doses during the whole study).

Partial or missing stop date will be imputed as follows:

If the stop date is completely missing and the event has resolved, or the subject has stopped taking the concomitant medication, the stop date will be imputed as the date of the subject's end of study visit

- If only the year is known, the stop date will be imputed as "31-Dec" of that year or as the date of the subject's last clinic visit in the study if in the same year.
- If the month and year are known, the stop date will be imputed as the last day of that month unless the stop date corresponds to the same month as the subject's last clinic visit in which case the date of subject's last clinic visit in the study will be used instead.

Missing start date will be imputed as follows:

- If the stop date occurs on or after the start of study drug or the event / concomitant medication is ongoing, the start date will be imputed as the date of the first dose of study drug.
- If the stop date occurs before the start of study drug, the start date of the event / concomitant medication will be imputed as the subject's screening date or the stop date of the event / concomitant medication whichever the earlier.

Partial start date (year present, but month and day missing) will be imputed as follows:

- If the stop date occurs on or after the start of study drug or the event / concomitant medication is ongoing, and the year is the same as the year of first dosing the start date will be imputed as "01-Jan" of the same year or the date of the first dose of study drug whichever is latest. If the year is different from the year of first dosing "01-Jan" will be used.
- If the stop date occurs before the start of study drug, the start date of the event / concomitant medication will be imputed as the "01-Jan" of the same year.

Partial start date (month and year present, but day missing) will be imputed as follows:

- If the stop date occurs on or after the start of study drug or the event / concomitant medication is ongoing, the start date will be imputed as the first day of the same month and year unless this partial start date is in same month as the first dose of study drug in which case the date of first dose of study drug will be used.
- If the stop date occurs before the start of study drug, the start date will be imputed as the first day of the month and year of the partial stop date.

All dates presented in the individual subject listings will be as recorded on the eCRF.

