## 5 RANDOMIZATION

This study is not randomized.

Subjects will receive DYN101 in a low (1.5 mg/kg), middle (4.5 mg/kg) or high (9 mg/kg) dose level in Cohorts 1, 2 and 3, respectively. In the MAD part, subjects may receive a different dose than what they received in the SAD part. In each cohort, there will be up to 6 subjects with a mutation in DNM2 (sub-cohort a) and up to 3 subjects with a mutation in MTM1 (sub-cohort b).

Cohorts will be enrolled in a sequential, staggered approach, with an interval of at least 7 days between dose administration of the first and second subject in a cohort, irrespective of their subcohort. The 48-hour safety data from the first subject in a cohort will be reviewed by the medical monitor before the next subject can be dosed. In addition, any SAE data from the first subject received up until the moment of treatment of the second subject will be taken into account.

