### **6.14.1 Adverse Events**

Adverse events will be reported separately for SAD and MAD + MAD Extension parts.

A pre-therapy AE is defined as any AE that starts before the first dose of study drug.

A treatment emergent adverse event (TEAE) is defined as:

- Any AE that has an onset on or after the first dose of study drug and before last dose of study drug + 28 days.
- Any pre-existing AE that has worsened in severity on or after the first dose of study drug and before the last dose of study drug + 28 days.

A treatment-related AE is defined as an AE as being related to the study drug. If an AE has missing relationship it is assumed to be related to the study drug for analysis purposes.

Maximum severity will be assumed for an AE with missing severity.

The following tables will be presented for AEs:

- Summary of All Adverse Events, incidence and the number of events.
- Pre-therapy AEs by system organ class and preferred term, incidence and number of events
- TEAEs by system organ class and preferred term, incidence and number of events
- Treatment-related TEAEs by system organ class and preferred term, incidence and number of events

- Serious TEAEs by system organ class and preferred term, incidence and number of events
- TEAEs leading to treatment withdrawal by system organ class and preferred term, incidence and number of events
- All AEs of special interest by system organ class and preferred term, incidence and number of events
- TEAEs by system organ class, preferred term and maximum severity, incidence
- Treatment related TEAEs by system organ class, preferred term and maximum severity, incidence
- TEAEs by system organ class, preferred term and study drug relationship, incidence
- Listing of Deaths (presented in the Table section of the appendices)
- Listing of Serious TEAEs (presented in the Table section of the appendices)

All AEs will be listed.

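### SAP 6.2.6 sets no lower bound at the first MAD dose, so MAD adverse events with a missing start, or only the year of first dosing, default to the SAD dose date

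*SAP*

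**What the plan says.** SAP 6.2.6 opens with a principle for AEs whose treatment-emergent status is unclear: "it will be assumed that the AE occurred after first dosing (earliest date of all doses during the whole study". The detailed start-date rules follow. For an event that is ongoing, or that stopped on or after the first dose, they are:

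- **Start completely missing:** "the start date will be imputed as the date of the first dose of study drug".
- **Year only, same year as first dosing:** 1 January "of the same year or the date of the first dose of study drug whichever is latest".
- **Year only, other years:** the sentence beginning "If the year is different from the year of first dosing" defaults to 1 January.
- **Month and year:** "the start date will be imputed as the first day of the same month and year unless this partial start date is in same month"; the exception covers only the month of first dosing, for which the first-dose date is used.

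None of these rules refers to the first MAD dose.

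The analysis, by contrast, has two periods. SAP 6.14.1 states: "Adverse events will be reported separately for SAD and MAD + MAD Extension parts". SAP 6.14 presents safety by the treatment received. SAP 5 adds: "In the MAD part, subjects may receive a different dose than what they received in the SAD part". The primary endpoint (SAP 3.1) is AE frequency and severity by dose, for single and multiple administration. The treatment-emergent definition in SAP 6.14.1 is study-wide: "onset on or after the first dose of study drug and before last dose of study drug + 28 days". The SAP does not say how an AE is assigned to a part.

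**The concern.** The imputation has one dose anchor and the tables have two parts. For any subject dosed in SAD, the earliest dose in the study is the SAD dose. A MAD event with too little date information is therefore dated to the SAD dose, months before the treatment during which it arose. If part follows onset date, the event leaves the multiple-dose table and enters the single-dose table. Where the subject changed dose between parts, it also appears under a dose the subject was no longer receiving.

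Replacement subjects who enter directly at MAD (Protocol 3.1.2 and 6.1.3.3) have a MAD dose as their first dose. The same missing start is therefore handled differently according to how the subject reached MAD.

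This bears on what the abbreviated report still delivers. SAP 8 retains the full safety analyses, and the AE tables remain in SAP 12.

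**Working it through.** The plan gives no figure to reproduce, so the check applies the rules to dates.

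**Inputs from the documents**
- Gap from SAD dose to MAD: 4 weeks of follow-up plus at least 12 weeks of washout (SAP 1).
- MAD treatment: 12 weeks, plus 12 weeks of extension.
- About 6 subjects per dose level, with up to 3 MTM1 subjects (SAP 4).

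**Gap.** 4 + 12 = 16 weeks; 16 × 7 + 1 = Day 113, which agrees with the SAD W17 column of the Trial Schedules. A MAD event therefore cannot share a calendar month with the SAD dose, so the same-month exception never reaches it.

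**Rules.** Let A be the first dose in the study and M the first MAD dose. For a true onset on or after M, the imputed start is:
- missing: A
- year only, year of A: max(1 January, A) = A
- year only, later year: 1 January
- month and year: first of that month

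The event leaves MAD when the imputed start is before M.

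**Illustration** (dates assumed): A = 10-Mar-2020, M = 08-Sep-2020.

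| True onset | Start missing | Year only | Month and year |
|---|---|---|---|
| 18-Sep-2020 | 10-Mar-2020, before M | 10-Mar-2020, before M | 01-Sep-2020, before M |
| 18-Oct-2020 | 10-Mar-2020, before M | 10-Mar-2020, before M | 01-Oct-2020, in MAD |
| 26-Jan-2021 | 10-Mar-2020, before M | 01-Jan-2021, in MAD | 01-Jan-2021, in MAD |

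**How often each pattern crosses.** The rules were applied to every onset day in MAD. The assumptions, none of them from the documents, were SAD dates uniform over two years, a SAD-to-MAD gap of 16 to 52 weeks, and onset uniform over 12 or 24 weeks of MAD. Share of MAD-onset events dated before M:

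| Date pattern | 12 weeks | 24 weeks |
|---|---|---|
| Start missing | 100% | 100% |
| Year only, all | 88% | 77% |
| Month and year | 18% | 9% |

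Within the year-only row, the share is 100% when the year is that of first dosing. In a later year it runs from 57% to 88%, depending on the gap and the window.

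Rough hand checks agree. A year-only event stays in MAD only if onset follows a New Year that falls after M. The average onset is half the window after M, so the crossing share is about 1 − 42/365 = 88% over 12 weeks and 1 − 84/365 = 77% over 24 weeks. A month-and-year event crosses only in the calendar month in which MAD starts, where about 15 days remain on average: 15/84 = 18% and 15/168 = 9%.

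These shares are conditional on a date being incomplete. They do not predict how many events will be affected.

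**Effect of one event.** The event count moves by one. The subject incidence moves by 1/6 = 17 percentage points in a cohort of 6, or 1/3 = 33 points in a sub-cohort of 3, and only if the subject has no other qualifying event in that cell.

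**The case against.** **Part assignment is not stated.** The SAP could be implemented using the eCRF visit or period instead of onset date, and the misplacement would then not arise. This stands, so the conclusion is conditional. It does not clear the plan, because no other rule is given and the tables need one. Applying the 28-day limit within each part would not help either. In the illustration, an event dated 01-Sep-2020 would fall outside a SAD window ending 07-Apr-2020, yet it would still not be in MAD.

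**The worst patterns are the least likely.** AEs are asked about at every visit (Protocol 6.2.2.1), and MAD visits are weekly, so a new event can usually be placed within about a week. The SAP itself does not expect missing dates. This stands and limits the size of the problem.

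**The analysis is descriptive, and listings show dates as recorded.** A careful reader of about 18 subjects' listings could spot a misplaced event. That is a safeguard, but the tables carry the primary endpoint.

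**Two stronger readings are not supported.** A reader might infer that every incomplete MAD date is pulled back to the SAD dose. The 1 January and first-of-month defaults show otherwise, and about 82% to 91% of day-missing MAD events stay in MAD under the assumptions above. A reader might also infer that the SAP's claim to be conservative is false. That claim concerns whether an event is treatment-emergent, and there it works: the imputed event stays within the study-wide treatment-emergent definition. The SAP makes no such claim about allocation between parts.

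**Conclusion.** The concern holds in a limited form. If events are assigned to a part by onset date, a MAD event in a subject first dosed in SAD is counted in SAD whenever its start is completely missing, or when only the year is known and it is the year of first dosing. Year-only starts in a later year, and month-and-year starts, cross only when 1 January or the first of the month precedes the first MAD dose.

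Misplaced events leave the multiple-dose count. They carry a wrong dose label only where the SAD and MAD doses differ; otherwise the error is confined to single versus multiple administration. Replacement subjects who start in MAD are unaffected.

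The number should be small, but the rule gives a wrong allocation on the primary endpoint when followed as written. It should be corrected before the tables are produced.

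**What to change.** In SAP 6.2.6 and 6.14.1:

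1. State that AEs are assigned to SAD or to MAD plus MAD Extension by onset date, imputed where necessary.
2. Add a part-specific lower bound. It applies if the known date parts and the stop date allow an onset on or after the first MAD dose, and the AE was first reported after that dose was given. In that case, impute the later of the current rule's date and the first MAD dose date. Otherwise keep the current rule.
3. Attribute the event to the dose received at the imputed onset.
4. Flag imputed onsets in Listing 16.2.7.1, still showing the recorded dates.

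The wording in step 2 must exclude events reported at the pre-dose MAD Day 1 assessment. The MAD schedule collects AEs that day and places the assessments before dosing, so a cut-off of at or after MAD Day 1 would pull pre-dose events into MAD.

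In the illustration, if all three events were first reported after the first MAD dose, every imputed start would fall on or after 08-Sep-2020.

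The cost is a few sentences and a small program change, with no new assessments. SAP 6.2.7 already uses the first MAD dosing date. The visit or date of first report must be retrievable; the documents do not say whether the AE form records it, but so few events could be resolved by hand.
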